**Estrogen Receptor Antagonist in Patients with
Pulmonary Arterial Hypertension
(ERA PAH)**

Protocol

July 18, 2016

Version 1.0

**[name], MS
Perelman School of Medicine at the
University of Pennsylvania
Principal Investigator**

Protocol Summary

OBJECTIVES:

- To determine changes in circulating hematopoietic progenitor cells, plasma hormone levels, NT-proBNP, and other plasma biomarkers after the administration of fulvestrant in subjects with pulmonary arterial hypertension.
- To observe changes in tricuspid annular plane systolic excursion, stroke volume index, right ventricular fractional area change, and other echo parameters after fulvestrant administration.
- To determine changes in distance walked in six minutes after fulvestrant administration.
- Safety and side effects associated with fulvestrant administration in subjects with pulmonary arterial hypertension.

STUDY DESIGN:

Phase II single-arm, open-label study of fulvestrant in five post-menopausal women with pulmonary arterial hypertension for twelve weeks.

STUDY POPULATION:**Inclusion criteria:**

- Previous documentation of mean pulmonary artery pressure > 25 mm Hg with a pulmonary capillary wedge pressure (or left ventricular end-diastolic pressure) < 16 mm Hg and pulmonary vascular resistance > 3 WU at any time before study entry.
- Diagnosis of PAH which is idiopathic, heritable, drug- or toxin-induced, or associated with connective tissue disease, congenital heart disease, portal hypertension, or HIV infection.
- Most recent pulmonary function tests with FEV1/FVC >50% AND either a) total lung capacity > 70% predicted or b) total lung capacity between 60% and 70% predicted with no more than mild interstitial lung disease on computerized tomography scan of the chest.
- Female, post-menopausal state, defined as:
 - > 50 years old and a) have not menstruated during the preceding 12 months or b) have follicle-stimulating hormone (FSH) levels > 40 IU/L **or**
 - < 50 years and FSH > 40 IU/L **or**
 - having had a bilateral oophorectomy.
- Informed consent.

Exclusion criteria:

- Age < 18.
- Treatment with estrogen or anti-hormone therapy (tamoxifen, anastrozole, etc.)
- WHO Class IV functional status.
- History of breast cancer.
- Clinically significant untreated sleep apnea.
- Left-sided valvular disease (more than moderate mitral valve stenosis or insufficiency or aortic stenosis or

insufficiency), pulmonary artery or valve stenosis, or ejection fraction < 45% on echocardiography.

- Initiation of PAH therapy (prostacyclin analogues or receptor agonists, endothelin-1 receptor antagonists, phosphodiesterase-5 inhibitors, soluble guanylate cyclase stimulators) within three months of enrollment; the dose must be stable for at least 3 months prior to Baseline Visit. PAH therapy which is stopped and then restarted or has dose changes which are not related to initiation and uptitration will be allowed within 3 months prior to the Baseline Visit.
- Hormone therapy.
- Use of warfarin or other anticoagulant (use of aspirin is permitted).
- Platelet count <100,000.
- Renal failure (creatinine \geq 2.0).
- Child-Pugh Class C cirrhosis.
- Current or recent (< 6 months) chronic heavy alcohol consumption.
- Current use of another investigational drug (non-FDA approved) for PAH.

ENDPOINTS:

- Changes in right ventricular systolic pressure, right ventricular fractional area, stroke volume index and tricuspid annular plane systolic excursion
- Changes in six-minute walk distance
- Changes in plasma NT-proBNP and estradiol levels
- Assess safety and side effects associated with fulvestrant administration in subjects with pulmonary arterial hypertension

STUDY OBSERVATIONS:

- Subjects will be evaluated in person at screening, baseline, two weeks, four weeks, eight weeks and nine weeks.
- Subjects will have telephone follow-up at week twelve.
- Laboratory tests including a complete blood count, hepatic function panel, follicle-stimulating hormone, coagulation studies (PT/INR) will be performed at the screening visit.
- Research laboratories such as estradiol (E2) and NT-proBNP levels will be evaluated at baseline and repeated after nine weeks of fulvestrant administration.
- Subjects will have six minute walk testing at baseline and week nine.
- Subjects will have a transthoracic echocardiogram at screening or baseline and week nine.

SAMPLE SIZE AND POWER:

A total of 5 subjects will be enrolled to receive fulvestrant at baseline, two weeks, four weeks, and eight weeks. Formal power calculations were not performed as this study is intended to show feasibility and for hypothesis-generation.

DATA ANALYSIS:

The study endpoints will be evaluated using summary statistics and graphical tools. Univariate analysis will be performed for all variables of interest. These will be carried out by comparing the changes from baseline using signed rank tests for continuous variables and McNemar's test for categorical variables.

Brief Table of Contents

9.3.2 Chemistry.....	30
9.4 Fulvestrant -related laboratory abnormalities of drug interactions.....	30
9.5 Other events.....	30
9.6 Safety and Adverse Events.....	31
9.6.1 Definitions.....	31
9.6.2 Classifying adverse events.....	32
9.6.3 Interpretation of definitions.....	33
9.6.4 Reporting procedures for adverse events / unanticipated problems.....	34
9.6.5 Subject withdrawal.....	37
9.7 Confidentiality of study data.....	37
9.7.1 Global unique identifier	38
9.8 Potential risks.....	38
9.9 Potential benefits.....	39
9.10 Alternatives.....	39
9.11 Ethical Considerations.....	39
REFERENCES.....	40

ABSTRACT

Pulmonary arterial hypertension (PAH) is characterized by obliteration of the pulmonary vascular bed. Right-sided heart failure ensues with severe limitation of exercise and eventual progression to death.

The role of female sex in PAH has long been recognized. Certain types of PAH are more common in women and some have implicated hormone therapy in causing or worsening PAH. A genetic study has shown that variation in estrogen metabolism is a risk factor for PAH. These data strongly suggest estrogen as a potential therapeutic target in the treatment of PAH.

Fulvestrant is an FDA-approved estrogen receptor (ER) antagonist, used to treat postmenopausal women who are diagnosed with hormone receptor-positive metastatic breast cancer. Fulvestrant binds to ER in a competitive manner and downregulates the ER protein. We aim to determine if fulvestrant will decrease circulating pro-angiogenic hematopoietic progenitors in the plasma and plasma estradiol levels as well as lower right ventricular systolic pressure in patients diagnosed with PAH.

Chapter 1. Background and Significance

1.1 Definition and characterization of PAH

Pulmonary arterial hypertension (PAH) is defined by a mean pulmonary artery pressure > 25 mm Hg, a pulmonary vascular resistance > 3 WU, and a normal pulmonary capillary wedge pressure. Endothelial thickening, smooth muscle hypertrophy, and *in situ* thrombosis are present in small pulmonary arteries, however the disease mechanism is unknown. The three year survival is only 60%.

1.2 Hormonal effects on the vasculature

In PAH, abnormal endothelial cell proliferation and expression of angiogenesis markers characterize the pulmonary vascular lesions. Animal models and patients with PAH have increased pro-angiogenic hematopoietic progenitor cells (HPCs) in the bone marrow and circulating in blood.¹ Estradiol stimulates HPC mobilization via the estrogen receptor α (ER α), and ER α blockade reduces HPC colony formation and endothelial growth.

Estradiol is metabolized by cytochrome P450 (CYP) enzymes to metabolites which have both pro-angiogenic (16 α -OHE1, signaling via ER α) and anti-angiogenic (2-OHE, 2-methoxyestradiol [2ME]) effects. The rs1800440 single nucleotide polymorphism (SNP) in CYP1B1 (enzyme that metabolizes estrone) produces a higher urinary 16 α -OHE1/2-OHE ratio, and both the SNP and urinary ratio are risk factors for heritable PAH.²

Androstenedione and testosterone are converted by aromatase to estrone and estradiol (E2) which signal via ER α and β . Female sex and estrogen are traditionally thought to have beneficial effects on the lung vasculature. Estrogen attenuates pulmonary vascular remodeling and right ventricular changes in hypoxic and monocrotaline animal models of pulmonary hypertension.³⁻⁵ These findings are however inconsistent with human PAH. First, female sex *increases* the risk of idiopathic and heritable PAH and portopulmonary hypertension.⁶ Austin et al. showed that subjects with certain genotypes of CYP1B1 had lower 2-hydroxyestrone:16 α -hydroxyestrone ratio and had a higher risk of PAH.² We have shown that SNPs in aromatase raised circulating E2 levels and increased the risk of PAH.⁷

E2 metabolites may also contribute to pathogenesis. CYP1B1 is highly expressed in the lung and oxidizes E2 to 2-OHE and then 2-ME which inhibits angiogenesis and endothelin-1.^{8,9} 16 α -OHE₁ increases DNA synthesis and cellular proliferation via ER α stimulation. The dominant hydroxylation pathway (affected in part by variation in the rs1800440 SNP (A>G, Asn453Ser) in CYP1B1) determines the ratio of these E2 metabolites. The rs1800440 CYP1B1 SNP is associated with a higher 16 α -OHE₁/2-OHE urinary ratio (the “readout” of CYP1B1) and with a higher risk for cancer, a finding attributed to enhanced angiogenesis. Accordingly, in the monocrotaline model of pulmonary hypertension, administration of 2-ME reduced vascular remodeling by > 50% and improved survival.¹⁰ All of the known vascular and angiogenic effects of estrogen

hormones act via ER α , making this the pivotal receptor in these processes. In summary, these data show that female sex and genetic variation in E2 production, activity, and metabolism are important risk factors for PAH. These findings implicate that the mechanistic pathway between estrogen signaling and PAH warrants exploration.

1.3 Fulvestrant and estrogen inhibition

Fulvestrant is an FDA-approved ER antagonist, used to treat postmenopausal women who are diagnosed with hormone receptor-positive metastatic breast cancer. Fulvestrant binds to ER in a competitive manner and downregulates the ER protein.

1.4 Summary

Data suggest that E2 may contribute to PAH. Treatment with fulvestrant, an ER antagonist, may therefore be effective in PAH.

Chapter 2. Objectives and Specific Aims

2.1 Objectives

This is a Phase II, open-label, single center, “proof of concept” study to examine the feasibility and effects of fulvestrant in post-menopausal women with PAH.

2.2 Specific Aims

1. To determine changes in circulating hematopoietic progenitor cells, plasma hormone levels, NT-proBNP, and other plasma biomarkers after the administration of fulvestrant in PAH.
2. To observe changes in tricuspid annular plane systolic excursion, stroke volume index, right ventricular fractional area change, and other echo parameters after fulvestrant administration.
3. To determine changes in distance walked in six minutes after fulvestrant administration.
4. Safety, feasibility and side effects associated with fulvestrant administration in subjects with PAH.

Chapter 3. Screening, Subject Selection

3.1 Recruitment

3.1.1 Identification and screening process

Subjects will be identified by the PH clinicians who care for patients with PAH at Penn Medicine. We expect to screen approximately 200 subjects over 12 months. Potentially eligible subjects will be approached about the study at a regularly scheduled PH clinic visit. After the initial screening, the subject will be provided a consent form before any study procedures are performed.

3.2 Subject selection criteria

3.2.1 Inclusion criteria

- Previous documentation of mean pulmonary artery pressure > 25 mm Hg with a pulmonary capillary wedge pressure (or left ventricular end-diastolic pressure) < 16 mm Hg and pulmonary vascular resistance > 3 WU at any time before study entry.
- Diagnosis of PAH which is idiopathic, heritable, drug- or toxin-induced or associated with connective tissue disease, congenital heart disease, portal hypertension, or HIV.
- Most recent pulmonary function tests with FEV1/FVC >50% AND either a) total lung capacity > 70% predicted or b) total lung capacity between 60% and 70% predicted with no more than mild interstitial lung disease on computerized tomography scan of the chest
- Women who are post-menopausal, defined as: 1) > 50 years old and a) have not menstruated during the preceding 12 months or b) have follicle-stimulating hormone levels > 40 IU/L or 2) < 50 years and follicle-stimulating hormone levels > 40 IU/L, or 3) having had a bilateral oophorectomy.
- Informed consent.

3.2.2 Exclusion criteria

- Age < 18 years
- Treatment with estrogen or anti-hormone therapy (tamoxifen, anastrozole, etc.)
- WHO Class IV functional status.
- History of breast cancer.
- Clinically significant untreated sleep apnea diagnosed by polysomnography.

- Left-sided valvular disease (more than moderate mitral valve stenosis or insufficiency or aortic stenosis or insufficiency), pulmonary artery or valve stenosis, or ejection fraction < 45% on echocardiography.
- Initiation of PAH therapy (prostacyclin analogues or receptor agonists, endothelin-1 receptor antagonists, phosphodiesterase-5 inhibitors, soluble guanylate cyclase stimulators) within three months of enrollment; the dose must be stable for at least 3 months prior to Baseline Visit. PAH therapy which is stopped and then restarted or has dose changes which are not related to initiation and up-titration will be allowed within 3 months prior to the Baseline Visit.
- Hospitalized or acutely ill.
- Use of warfarin or other anticoagulant (use of aspirin is permitted).
- Platelet count <100,000.
- History of bleeding disorder.
- Renal failure (creatinine \geq 2.0).
- Child-Pugh Class C cirrhosis.
- Current or recent (< 6 months) chronic heavy alcohol consumption.
- Current use of another investigational drug (non-FDA approved) for PAH.

Chapter 4. Treatment

4.1 Fulvestrant

Fulvestrant is given intramuscularly (IM). Steady state concentrations are reached within the first month and plasma levels are maintained for at least one month. It is metabolized by the liver as well as multiple biotransformation pathways. Metabolites are less active or have similar activity to parent compound.

The majority of clinical studies have been conducted in patients with estrogen-positive breast cancer such as the Comparison of Faslodex in Recurrent or Metastatic Breast Cancer (CONFIRM) trial, a randomized, double-blind, phase III trial that enrolled 746 women. Patients were randomly assigned to fulvestrant at two doses: 500 mg or 250 mg at days 0, 14, 28 and every 28 days.

The CONFIRM trial suggested that fulvestrant 500 mg is superior to fulvestrant 250 mg. The researchers found that there was a 19% reduction in risk of death and a 4.1 month difference in overall survival in subjects who were randomized to 500 mg fulvestrant dosage compared with fulvestrant 250 mg. The higher dose was well tolerated with no new safety concerns. Patients with Child-Pugh Class B liver disease could be safely given doses of fulvestrant 250 mg.

This study will utilize fulvestrant 500 mg administered intramuscularly into the buttocks slowly (1-2 minutes per injection) as two 5 mL injections, one in each buttock, on days 0, 14, 28 and 56. Fulvestrant 250 mg (one 5 mL injection) will be used in patients with Child-Pugh Class B liver disease.

4.2 Management of other medical therapies during the trial

The subjects' pre-study medical regimen will be continued after enrollment in the study. There will be no constraints on the management of the subjects' PAH medication during the study period.

Chapter 5. Data Collection

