5.1.6 Visit 5 (Nine weeks -3 or + 7 days)

The research coordinator will call the subject 1-2 days before the visit as a reminder. The coordinator will instruct the subject to not eat or drink (except water) and to avoid heavy exercise for 12 hours before the study day assessment. Subjects will be instructed

to bring a list of the current medications and to take all medications before the visit other than any oral PAH medication(s). The subject should bring their oral PAH medication(s) with them to be taken after the blood draw. The subject will be reminded to wear appropriate clothing and shoes to complete a 6MWT.

The subject will arrive at the study site outpatient clinic. The following procedures will be performed:

- Labs/Phlebotomy: research labs
- Echocardiogram
- Interim medical history
- Assess any adverse events/serious adverse events
- Vital signs
- Review current medications
- WHO functional class assessment
- Physical exam
- 6MWT with Borg scores

There is no particular order in which these procedures must be done, but it is recommended that the fasting blood draw be performed first.

Blood samples for study assays will be processed and banked. After obtaining the blood samples, the subject will be instructed to take their regular medications.

Echocardiography will be performed. The investigator or research nurse will take a history and perform a physical examination. The subject will complete the 6MWT.

The research coordinator will thank the subject for their participation in the clinic visits of the clinical trial. A follow-up phone call will be scheduled.

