5.1.7 Follow-up Phone Call (Twelve weeks ± 3 days)

The research coordinator will call the subject. The following will be reviewed:

- Any changes in concomitant medication
- Review all adverse events/serious adverse events
- Interim medical history

If there is a significant increase in symptoms or worsened clinical status the subject will be asked to come to the study center for evaluation.

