5.2 Study schedule of procedures

The table below summarizes the study procedures.

Table 1. Study Procedures

	Screening*	Baseline	Week 2	Week 4	Week 8	Week 9	Week 12 Follow-up Phone Call
Visit #		1	2	3	4	5	
Day#	-28 - 0	-2 - 0	14 ± 3	28 ± 3	56 ± 3	- 3- (63) + 7	84 ± 3
Informed consent	X						
General Testing							
Physical Exam		X		X		X	
Medical history	X	X ^a					
Vital signs	X	X	X	X	X	X	
WHO FC Assessment		X		X		X	
Laboratory Test							
Complete blood count	X	X ^a					
Hepatic function panel	X	X ^a					
Coagulation studies (PT/INR)	X	X ^a					
FSH	X	X ^a					
Research labs		X				X	
Study procedures							
Study drug administration		X	X	X	X		
Echocardiogram	X	X ^a				X	
Six minute walk test		X				X	
Concomitant Medications	X	X	X	X	X	X	X
Assess Adverse Events/Serious Adverse Events		X	X	X	X	X	X

X^a: Only to be performed if not done at screening visit. These assessments should be reviewed by the PI prior to first administration of study drug to ensure that the subject meets inclusions/exclusion criteria.

*Screening Visit procedures may be done at the Baseline Visit for female participants who are known to be post-menopausal: (1) > 50 years old and have not menstruated during the preceding 12 months or (2) have undergone bilateral oophorectomy. Review of medical history, medications, and informed consent must be obtained prior to the combined visit.

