7.1 Study design

To address the aims of this study, we will conduct an open-label, single-arm trial. Blood sampling, echocardiography and 6MWT will be performed at baseline and nine weeks.

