7.3 Statistical procedures

7.3.1 Data analysis

Prior to the formal analysis, the distributions of the key variables to be used in the analyses will be examined using summary statistics and graphical tools.

Outcomes of interest will be evaluated with a per-protocol analysis. Subjects who are not compliant or stop the treatment portion of the study will be replaced (although their data will also be considered in secondary analyses). Outcomes include estradiol levels, TAPSE and other echocardiographic measures, 6MWD, plasma NT-proBNP level, and other variables as well as safety and side effects.

These measures will be assessed both at baseline and nine weeks. Summary statistics will be produced with both the repeated measures as well as the calculated differences from the baseline. We will summarize demographics and other predictors of clinical status. Continuous variables will be summarized by the mean, median, standard deviation, and range, as appropriate. We will use contingency tables for discrete and dichotomous variables.

Hypothesis testing will use two-sided $\alpha= 0.05$. All statistical analyses will be performed using SAS and R.

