9.5 Other events

We will not discontinue study drug for clinical events not thought to be serious drug-related AEs. For example, a hospitalization for clinical worsening will not result in cessation of trial participation. Such events could result in missing data for primary and secondary endpoints, comprising the integrity of the analysis. As the trial does not prohibit any therapies which is the standard of care in PAH, there is no ethical or safety reason to stop trial participation under such circumstances. Even if subjects are withdrawn from the study drug outcome assessments will continue. Subjects who are not compliant or stop the treatment portion of the study will be replaced.

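### Does the freedom to change PAH therapy during the study call for an analysis rule in Chapter 7?

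*Combined protocol and SAP*

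**What the plan says.** Section 4.2 continues each subject's existing regimen and then leaves it open to change: "There will be no constraints on the management of the subjects' PAH medication during the study period". Section 9.5 shows that this is deliberate. Subjects stay in the trial through clinical worsening, with the reason given as "As the trial does not prohibit any therapies which is the standard of care in PAH". It also gives an analytic motive for not ending participation: "Such events could result in missing data for primary and secondary endpoints".

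Medication is tracked throughout. The row "Concomitant Medications" in Table 1 (section 5.2) is marked at screening, baseline, weeks 2, 4, 8 and 9, and the week-12 call. Section 5.1.6 lists "Review current medications" at the week-9 outcome visit, and section 5.1.7 covers "Any changes in concomitant medication" at week 12.

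On analysis, section 7.1 describes a single open-label arm and states: "Blood sampling, echocardiography and 6MWT will be performed at baseline and nine weeks". Section 7.3.1 adds: "Outcomes of interest will be evaluated with a per-protocol analysis". It plans means, medians, standard deviations and ranges, and section 7.3.2 plans signed rank and McNemar tests of change from baseline. Section 7.4 says that the study is for hypothesis generation and feasibility. No part of Chapter 7 mentions PAH or other concomitant medication.

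**The concern.** With no control arm, anything that changes between baseline and week 9 is mixed with the effect of fulvestrant. Background PAH therapy is an obvious candidate. Added therapy could hide a decline or produce an apparent gain in walk distance, right ventricular measures or NT-proBNP, and a reduction could look like harm. With five subjects, one such case carries weight.

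The protocol itself treats therapy changes as relevant before baseline, through the stability criterion in section 3.2.2, but does not return to them in the analysis. The main analysis is per-protocol and that set is not defined. One might therefore fear that a subject whose therapy changed could be kept or dropped after the open-label results are seen.

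**Working it through.** The plan gives no power, effect size, standard deviation or rate of therapy change, so there is no figure of its own to reproduce. The check has five steps.

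**1. Is the information collected?** Yes. Table 1 schedules concomitant medications at all seven contacts, including the week-9 outcome visit.

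**2. Could a therapy change remove a subject?** The stated grounds for replacement are:
- non-compliance or stopping treatment (sections 7.3.1 and 9.5);
- dropping out of treatment or assessments (section 7.3.3).

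A change that section 4.2 expressly permits is none of these. Section 9.5 says that hospitalization for worsening does not end participation, and section 9.6.5 keeps subjects on study medication through worsening. Section 7.3.1 also sends the data of replaced subjects to secondary analyses. Read together, these sections already keep such a subject in.

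**3. How large could the distortion be?** Let *k* of the five subjects have a therapy change that shifts the outcome by *d* in the same direction. The shift in the mean is *k* × *d* / 5. Assume *d* = 20 to 50 m of six-minute walk distance:
- *k* = 0: 0 m
- *k* = 1: 20/5 to 50/5 = 4 to 10 m
- *k* = 2: 40/5 to 100/5 = 8 to 20 m

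If each subject has probability *p* of such a change by week 9, the chance that at least one is affected is 1 − (1 − *p*)^5:
- *p* = 0.05: 1 − 0.95^5 = 0.226
- *p* = 0.10: 1 − 0.90^5 = 0.410
- *p* = 0.20: 1 − 0.80^5 = 0.672

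The expected one-direction shift is *p* × *d*, from 0.05 × 20 = 1.0 m to 0.20 × 50 = 10 m. These figures give every change its full effect by week 9 whenever it occurred, so they are upper-end values for the assumed *d*.

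As an illustration, take changes of −20, −10, 0, 10 and 20 m (mean 0, median 0). Adding 50 m to the highest gives a mean of 50/5 = 10 m and a maximum of 70 m, with the median still 0. Adding 50 m to the lowest instead gives −10, 0, 10, 20 and 30 m, with mean and median both 10 m.

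**4. Does a test result turn on it?** With five subjects there are 2^5 = 32 sign patterns. The smallest exact two-sided signed rank p-value is 2/32 = 0.0625, and the smallest exact McNemar p-value is also 2 × 0.5^5 = 0.0625. Neither can reach the planned 0.05. Only uncorrected large-sample versions could fall below it (0.043 and 0.025 at the extreme). The results will be read descriptively.

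**5. What would added text alter?** A statement that permitted changes do not remove a subject repeats what step 2 finds. A per-subject listing leaves every mean, median, range and p-value as it was. It would show which outcome changes coincide with a therapy change, but not how much of each is due to that therapy.

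**The case for a change.** The best case for acting is that the five individual changes are the study's main product, so a reader needs to know which coincide with altered therapy, and nothing commits the investigators to show it. General wording in section 7.3 about predictors of clinical status and variables of interest does not name therapy. The violation record in section 7.6 would not catch a permitted change. Two sentences and one short listing would cost little.

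Much of this stands as fact. Chapter 7 is silent, and a listing would be good reporting. The undefined per-protocol set is also real, but it is a wider gap that is not specific to PAH therapy. The risk that it is used to drop these subjects is small, given the stated replacement grounds.

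Other parts are weaker. Worsening of a pre-existing condition is recorded as an adverse event (section 9.6.3), so therapy added because of worsening would often leave a trace there; changes for other reasons would not. WHO functional class is also assessed at week 4 (section 6.1.6), so week 9 is not the only reading after baseline.

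The proposed listing may also cost more than it seems. The reminders at weeks 2, 4 and 8 name only new medications, whereas screening and baseline also name dose changes. No section says that the date or reason of a change is recorded. Current medications are still reviewed at each visit, so most changes can be recovered by comparing visits.

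A separate point is the PAH-therapy stability criterion in section 3.2.2, repeated in the Protocol Summary. One sentence requires stability and the next allows some restarts and dose changes in the same three months. The two must be reconciled, but that is a matter of eligibility wording and does not bear on the analysis.

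**Conclusion.** No change to the plan is needed. The omission is a reporting detail that analysts can fill sensibly from records already scheduled, for five subjects, when results are written up. Leaving background therapy free is a fair trade-off, made openly to keep subjects in the trial and their outcomes observed. Its price is weaker attribution, which the single-arm design already carries and which no listing or rule in section 7.3 would restore.

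The possible shift in the mean walk change runs from nil to 10 m with one subject affected and 20 m with two. That rests wholly on an assumed effect of 20 to 50 m, the same direction in both subjects, and full effect by week 9. The judgement also assumes that the stated replacement grounds are applied as written, so that a permitted therapy change does not remove a subject from the main summary.
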